2. INTRODUCTION

Sjögren's Syndrome (SjS) is a slowly progressive systemic chronic autoimmune disorder characterized by lymphocytic infiltration of exocrine glands causing lacrimal and salivary gland dysfunction. Clinical presentation varies from mild symptoms such as dry eyes (keratoconjunctivitis sicca) and dry mouth (xerostomia), arthralgia, and chronic fatigue, to severe systemic symptoms, involving multiple organ systems (1). In more than 30% of cases, extra-glandular systemic disease manifestations can develop, such as arthritis, nephritis, cytopenia, pneumonitis, vasculitis, and neurological complications. Furthermore, subjects suffering from SjS have a marked increased risk of lymphoma (2,3). Disabling fatigue and loss of working productivity negatively affect the patient's quality of life (QoL). The disease may occur as a primary form (primary Sjögren's Syndrome [pSS]) or as a secondary form associated with other conditions (most commonly rheumatoid arthritis [RA] and systemic lupus erythematosus [SLE]). The estimated prevalence is 0.06% worldwide. It is known to affect perimenopausal women more frequently than men and more frequently and more severely Caucasians than other races (1,3).

Although disease pathogenesis has not yet been fully elucidated, substantial data has demonstrated that abnormal autoimmune responses involve innate and adaptive immunity, possibly triggered by viral infections and hormonal factors in genetically predisposed individuals. Salivary gland epithelial cells, alongside cluster of differentiation 4 (CD4+) T-lymphocytes and also B-lymphocytes, activated and/or stimulated by interferons and other cytokines may thus trigger and maintain chronic immune activation resulting in a vicious cycle of autoimmunity. Furthermore, a range of autoantibodies can be present in SjS (anti-SSA/Ro and anti-SSB/La antibodies, rheumatoid factor, cryoglobulins, anti-nuclear antibodies), complicating the presentation (4,5). There is also a potential role of immune factors that influence central nervous system (CNS) behavior with an impact upon efferent neuronal pathways that stimulate secretory glands (6). In addition to immune mechanisms, several non-immune factors may be involved in the pathogenesis (5).

Currently, there is no cure, nor an efficacious systemic immunomodulatory agent for the treatment of pSS. The goals of therapy in patients with pSS are symptom palliation, prevention of complications, management of systemic manifestations, and glandular and lymphoproliferative disease. The treatment of sicca symptoms alone, without glandular enlargement or other organ involvement, generally does not require systemic therapy other than secretagogues (pilocarpine, cimeviline). Steroids and typical disease-modifying antirheumatic drugs (DMARDs) have often limited efficacy, and there is no pharmacological intervention against the fatigue. Hence, the unmet medical need for more-effective treatment options is significant. Novel biological therapies may directly intervene with the pathophysiology of the syndrome and thus improve glandular and extraglandular manifestations of pSS (7,8). Oral, small-molecule inhibitors of intracellular kinases might bring therapeutic benefit in a wide range of inflammatory diseases, including pSS (9).

GLPG3970 has a dual mechanism of action with the potential to improve upon the currently available treatments, via the induction of immunoregulatory mechanisms in addition to its anti-inflammatory properties. GLPG3970 is an oral, selective, small-molecule serine/threonine salt-

inducible kinase (SIK) 2 and 3 inhibitor. These kinases provide a molecular switch in the control of pro- and anti-inflammatory cytokine production. Inhibition of these targets blocks the production of pro-inflammatory cytokines such as tumor necrosis factor alpha [TNF α], interleukin [IL]-12, and increases IL-10 levels, which has a tolerogenic role, by skewing macrophages and dendritic cells toward regulatory and tolerogenic phenotypes.

For more details refer to the latest version of the investigator's brochure (IB) and its relevant updates/addenda.

This clinical study will be conducted in compliance with this clinical study protocol (CSP), the current International Council for Harmonisation of Technical Requirements for Pharmaceuticals for Human Use - Good Clinical Practice (ICH-GCP) Guideline E6, and applicable local ethical and legal requirements (see also Section 12).

2.1. Background - Nonclinical Studies

2.1.1. Nonclinical Pharmacokinetics

[REDACTED]

[REDACTED]

[REDACTED]

[REDACTED]

2.1.2. Safety Pharmacology

[REDACTED]

2.1.3. General Toxicology

2.1.4. Genotoxicity

2.1.5. Embryo-Fetal Development Toxicity

2.1.6. Phototoxicity

[figure not shown]

[figure not shown]
2.2. Background - Clinical Studies

[figure not shown]
GLPG3970-CL-101 is an ongoing first-in-human (FIH) study conducted in healthy male subjects and subjects with psoriasis. In healthy volunteers, single ascending doses up to 500 mg q.d. and multiple ascending dosing up to 400 mg q.d. (oral solution, fasted conditions), as well as the

relative bioavailability of an initial exploratory solid formulation (capsules filled with mini-tablets) and the effect of food on the PK with both formulations have been completed, while the part in subjects with psoriasis is ongoing. The single and multiple ascending parts of the study were randomized, double-blind, and placebo-controlled to evaluate the safety, tolerability, pharmacokinetics (PK) [REDACTED] of GLPG3970 in adult healthy male subjects. The single ascending dose part evaluated GLPG3970 in the dose range 10 mg to 500 mg and in the multiple ascending dose part doses of 100 mg q.d., 250 mg q.d., and 400 mg q.d were evaluated over a period of 14 days.

Administration of GLPG3970 was well tolerated. No deaths, serious treatment-emergent adverse events (TEAEs), or TEAEs leading to study drug discontinuation were reported. No clinically significant abnormalities related to laboratory parameters, cardiovascular safety (electrocardiogram [ECG]), vital signs, or physical examination were reported.

Additional PK and safety data, as well as the compositions of the formulations are described in the latest version of the IB and its relevant updates/addenda.

3. CLINICAL STUDY OBJECTIVES

3.1. Primary Objectives

- To evaluate the efficacy of GLPG3970 compared to placebo on the signs and symptoms of pSS.
- To evaluate the safety and tolerability of GLPG3970 compared to placebo.

3.2. Secondary Objectives

- To further characterize the efficacy of GLPG3970 compared to placebo on the patient-reported signs and symptoms of pSS.
- To characterize the PK of GLPG3970.

3.3.

4. ENDPOINTS

4.1. Primary Endpoints

- Change from baseline in European League Against Rheumatism (EULAR) Sjögren's Syndrome Disease Activity Index (ESSDAI) score at Week 12.
 - Number, incidence, and severity of TEAEs.

4.2. Secondary Endpoints

- Change from baseline in EULAR Sjögren's Syndrome Patient Reported Index (ESSPRI) score at Week 4, 8, and 12.
 - Change from baseline in ESSDAI score over time at Week 4, 8, and 12.
 - Observed GLPG3970 C_{trough}.

4.3.

5. INVESTIGATIONAL PLAN

5.1. Clinical Study Design

This is a Phase 2a, randomized, double-blind, placebo-controlled, parallel-group, multicenter study to evaluate the efficacy, safety, tolerability, PK, [REDACTED] of orally administered GLPG3970 for 12 weeks in adult subjects with active pSS.

One dose level of GLPG3970 will be evaluated in 30 subjects who will be randomized 2:1 to receive GLPG3970 (400 mg [2 x 200 mg] q.d.) or matching placebo, respectively.

The study will consist of 3 study periods:

- Screening period: up to 4 weeks with 1 study visit. During the Screening visit, subjects will be selected based on the eligibility criteria. Subjects already on treatment will remain on a stable standard of care (SoC) treatment (see Section 6.1) during the study.
- Treatment period: 12 weeks with up to 5 study visits (Days 1, 8, 29, 57, and 85). At any time during the course of the study, phone calls or unscheduled visits can be added if deemed necessary by the investigator. Subjects will receive GLPG3970 or placebo q.d.
- Follow-up (FU) period: 4 weeks with 1 study visit. Subjects remain on stable SoC treatment, if applicable.

The subjects will be in the study for a duration of 20 weeks: up to 4 weeks of screening, 12 weeks of treatment, and 4 weeks of FU.

A schematic diagram of clinical study design and periods is provided in [Figure 2](#).

[figure not shown]

Figure 2: Schematic Diagram

For detailed information regarding dosage form, packaging, and labeling of the IP refer to Section 7.2, “[Dosage and Administration](#)” and Section 7.3, “[Packaging, Labeling and Distribution](#)”.

5.2. Start and End of Study Definitions

The study start is defined when the first informed consent form (ICF) is signed. The end of the study is reached when the last FU visit, as planned according to the Schedule of Activities (Section 8.11), for the last subject is performed.

5.3. Clinical Study Design Rationale

This is a first exploration of GLPG3970 in subjects with active pSS to evaluate the efficacy, safety, tolerability, PK profile [REDACTED]

The double-blind, randomized, parallel-group design is a standard design for a first study in subjects with active pSS.

Treatment duration of 12 weeks is considered adequate in order to explore the efficacy, safety, tolerability, PK, [REDACTED] in a study testing GLPG3970 for the first time in subjects with active pSS, and may support the future design of efficacy and safety studies in this population.

GLPG3970 is aiming to restore immune homeostasis in chronic inflammatory diseases through modulation of the immune system by altering the balance between effector and regulatory immune cells in the direction of tolerance. GLPG3970 may therefore also potentially decrease disease activity of pSS through induction of immunoregulatory mechanisms in addition to its anti-inflammatory properties. This is supported by nonclinical data obtained in various experimental models of autoimmune diseases. These data support the rationale for clinical evaluation of GLPG3970 in subjects with active pSS.

The use of a placebo arm in this type of design is widely regarded as the standard for testing the efficacy of new treatments. Subjects in the placebo arm can also be on stable SoC treatment since it is considered unethical to create a placebo group that will receive no treatment, if treatment is available.

5.4. Dosing Rationale

The dose of 400 mg q.d. GLPG3970, which was safe and well tolerated in healthy subjects, will be used in this study (see also Sections 2.1.3 and 5.5). [REDACTED]

[REDACTED]

[REDACTED]

[REDACTED]

[REDACTED]

[REDACTED]

5.5. Potential Risks and Benefits

GLPG3970 has been studied in a nonclinical setting (Section 2.1) in GLP studies in rat and dogs for a duration up to 13 weeks, and is being studied in a FIH study (Section 2.2) where the single ascending dose part has been completed up to the dose of 500 mg and the multiple ascending dose part up to 400 mg q.d. GLPG3970. Study GLPG3970-CL-207 is the first study where GLPG3970 is being administered to subjects with active pSS.

[REDACTED]

[REDACTED]

[REDACTED]

In the healthy volunteers part of study GLPG3970-CL-101, single doses of 10 to 500 mg GLPG3970 and repeated doses of 100 mg q.d., 250 mg q.d., 400 mg q.d. GLPG3970 administered for 14 days to healthy subjects were well tolerated. No death or SAE occurred during the study and no TEAEs led to study drug discontinuation. For more details refer to Section 2.2 and the latest version of the IB and its relevant updates/ addenda.

The most important potential risks based on in vitro and nonclinical studies, and the healthy volunteer part of study GLPG3970-CL-101 are: QT prolongation, hemato-lymphoid system toxicity, gastrointestinal toxicity, and risks related to fertility and pregnancy (see Section 2.1). Serious infections, including opportunistic infections and tuberculosis (TB) are also considered important potential risks based on the mechanism of action of the IP.

Specific for severe acute respiratory syndrome coronavirus 2 (SARS-CoV-2) infections, risk minimization measures have been implemented in this protocol, in order to prevent recruitment of subjects with active infection and to allow prompt intervention, in case a subject is presenting with signs and symptoms of SARS-CoV-2 infection.

GLPG3970 has a novel dual mechanism of action, which is intended to restore the balance of the immune system by reducing several mediators of inflammation and by improving immune-regulatory mechanisms that may be impaired in autoimmune diseases such as, for example, pSS, RA, psoriatic arthritis, and inflammatory bowel disease. This may weaken the immune response and can potentially increase subject's vulnerability to develop infections (e.g. opportunistic infections, SARS-CoV-2, etc.). Careful monitoring and reporting of signs and symptoms is therefore required, to enable prompt medical evaluation and pharmacological or clinical intervention.

Immunomodulatory therapies may affect subjects' immune response to vaccines, including Covid-19 vaccines. Available evidence suggests that routine vaccination is effective with most degrees of disease-related immune dysfunction and associated therapies. However, in absence of specific data on Covid-19 vaccination, and without an agreed correlate of protection for SARS-CoV-2, non-live vaccines should be administered according to local regulations.

The population targeted in the study focuses on subjects with active pSS. The dual mechanism of action of GLPG3970 has the potential to reduce the expression of pro-inflammatory cytokines upregulated in pSS and to induce the expression of immunoregulatory cytokines, thus offering the possibility of restoring homeostasis of the immune system. Subjects in the study may or may not derive benefit from administration of GLPG3970.

Risk Mitigation

Mitigation measures have been taken to ensure safety of the subjects targeting population selection, dose, concomitant medications, and safety surveillance on certain laboratory parameters [REDACTED]. Information on important safety risks is included in the latest version of the IB.

In the forthcoming study, subjects' risk will be minimized by implementing conservative eligibility criteria, by standard laboratory tests, and by collecting TEAEs throughout the study. Any potential negative effects of GLPG3970 will be carefully assessed through regular physical assessments and laboratory monitoring that will happen at every visit. Laboratory alerts will be set up for the study in order to early inform the study investigator and the sponsor on highly abnormal laboratory values (severity Grade 3 and above). A Safety Monitoring Committee will monitor unblinded data.

- [REDACTED]
- [REDACTED]
- [REDACTED]
- The selection of the dose proposed for this study lies within the exposure safety limits, defined based on nonclinical safety and toxicity studies, and exposures previously shown to be safe and well tolerated in healthy male subjects.
- [REDACTED]

Subjects at risk of TB, human immunodeficiency virus (HIV) positive subjects, subjects testing positive for HBV or HCV, and subjects tested positive for SARS-CoV-2 are excluded from the study.

Given this study will be performed during a SARS-CoV-2 pandemic, appropriate measures should be taken to minimize the risk of SARS-CoV-2 infection for subjects participating in the study as well as study site personnel. Local guidelines to prevent SARS-CoV-2 infection should be adhered to and a leaflet will be made available for subjects detailing the SARS-CoV-2 safety measures to be taken.

In case a randomized subject is not able to attend a scheduled study visit on site due to SARS-CoV-2 travel restrictions, a phone call or a televisit may be conducted. It is strongly recommended to conduct planned study assessments for the applicable visit as per protocol as much as possible. If possible and if local regulations allow and the subject agrees, trained study staff or trained personnel are encouraged to collect study assessments at the study subject's home or a local facility if social distancing and hygiene rules can be applied.

Only staff trained in conducting the protocol planned assessments are authorized to perform home or local facility visit assessments and the alternative arrangements need to be adequately documented. Direct to Patient (DTP) shipments are possible, if needed. Subjects presenting with signs and symptoms of infection, including SARS-CoV-2 infection, should immediately contact the site investigator, who should inform the sponsor's medical responsible as soon as possible, and SARS-CoV-2 testing should be performed.

5.6. Estimands

ICH draft guidance E9(R1) "*Statistical Principles for Clinical Trials: Addendum: Estimands and Sensitivity Analysis in Clinical Trials*" specifies that a central question for drug development and licensing is to quantify treatment effects: how the outcome of treatment compares to what would have happened to the same subjects under different treatment conditions (e.g. had they not received the treatment or had they received a different treatment). Intercurrent events need to be considered in the description of a treatment effect on a variable of interest because both the value of the variable and the occurrence of the event may depend on treatment. The definition of a treatment effect, specified through an estimand, should consider whether values of the variable after an intercurrent event are relevant, as well as how to account for the (possibly treatment-related) occurrence or non-occurrence of the event itself. More formally, an estimand defines in detail what needs to be estimated to address a specific scientific question of interest. A description of an estimand includes 4 attributes.

Indicated in italic are the attributes in the GLPG3970-CL-207 study for the primary estimand:

1. The population, that is, the patients targeted by the scientific question:
Patients with active pSS, defined through appropriate inclusion/exclusion criteria to reflect the targeted patient population for approval. Full Analysis Set (FAS), defined as all randomized subjects who have received at least 1 dose of IP.
2. The variable (or endpoint), to be obtained for each patient, that is required to address the scientific question:
Change from baseline in ESSPRI score at Week 12.
3. The specification of how to account for intercurrent events to reflect the scientific question of interest:
Early treatment discontinuation (any reason) is handled using the hypothetical strategy. Other intercurrent events (e.g. major protocol violations, intake of prohibited medication, lack of compliance) are handled using the treatment policy strategy (i.e. they are ignored).
4. The population-level summary for the variable which provides, as required, a basis for a comparison between treatment conditions:

Least square mean obtained using mixed model for repeated measurements (MMRM). For further details, see the study statistical analysis plan (SAP).

Together these attributes describe the primary estimand, defining the treatment effect of interest.

The design of the GLPG3970-CL-207 study targets this estimand as it is a randomized parallel-group study where every attempt is made to collect all measurements throughout the study.

Details on sensitivity analyses for the primary estimand or secondary estimands will be in the SAP.

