9. STATISTICAL METHODS

All statistical methods shall be detailed in a SAP that will be finalized prior to the database lock and unblinding. All relevant data collected in this clinical study will be documented using summary tables, figures, and subject data listings.

[figure not shown]
Any deviations from the CSP are to be justified in the SAP.

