9.1. Determination of Sample Size

Up to 30 subjects are planned to be randomized 2:1, i.e. 20 subjects will receive GLPG3970 (400 mg q.d.) and 10 subjects will receive placebo. In case of drop-outs due to SARS-CoV-2 infection, additional subjects may be randomized on top of the planned sample size. The number of additional subjects randomized will not exceed the number of subjects dropping out of the study in relation to SARS-CoV-2. Randomization of additional subjects will be decided by the sponsor before study lock or related unblinding has occurred.

This sample size provides favorable operating characteristics for the primary efficacy endpoint (i.e. ESSDAI change from baseline at Week 12) in terms of the modified signal detection methodology (21). This methodology will be used to provide further insight into the treatment effect of GLPG3970 over placebo, and will support scenario analyses. The posterior distribution of this treatment effect will be estimated, and from this distribution probabilities of reaching at least a certain effect (delta) will be derived, e.g. a range of plausible effect size values going from as high as $P(\delta \leq -5)$ to as low as $P(\delta \leq -2)$. A common SD of 4 was assumed for both active and placebo arm.

Probability	Reference value	Outcome
0.852	-5	Signal detected
0.041		No conclusion
0.107		Signal not detected
0.427	-3	Signal detected
0.088		No conclusion
0.485		Signal not detected
0.205	-2	Signal detected
0.050		No conclusion
0.745		Signal not detected

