9.3.4.1. Analysis for Primary Efficacy Endpoint

The signal detection methodology described by Frewer et al (21) will be used to provide further insight into the treatment effect of GLPG3970 over placebo, and will support scenario analyses. See also Section 9.1.

A MMRM (ESSDAI) will be used to compare treatment groups, with a 90% confidence interval (CI) of the treatment difference at Week 12.

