## 1. INTRODUCTION

This statistical analysis plan (SAP) describes the final statistical analyses of study GLPG3970-CL-207. The results of the analysis will be described in the clinical study report (CSR).

Technical details on derivations and mock tables, listings and figures (TLFs) will be presented in a separate document.

The statistical analysis will process and present the results following the International Council for Harmonization (ICH) standards, particularly the ICH-E3, ICH-E6, ICH-E9, ICH-R9 (R1) and ICH-E14 guidelines.

On 26 November 2021, the Safety Monitoring Committee recommended to immediately terminate Study GLPG3970-CL-207 due to a safety signal of liver toxicity. Therefore, the GLPG3970-CL-207 study was prematurely stopped. In view of this, only the primary endpoint and safety analyses will be performed. Results will be presented in an abbreviated CSR. Any provisions no longer applicable following premature study termination are highlighted in grey.

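### Does the protocol's naming of ESSPRI in the primary estimand put the ESSDAI primary analysis in doubt?

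*Protocol*

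**What the plan says.** Protocol Section 5.6 sets out the four attributes of the primary estimand. The second, the variable, is given as "Change from baseline in ESSPRI score at Week 12". The section closes by saying that "The design of the GLPG3970-CL-207 study targets this estimand".

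The rest of the protocol points elsewhere:

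- Section 4.1 lists as the primary efficacy endpoint the change from baseline in the EULAR Sjögren's Syndrome "Disease Activity Index (ESSDAI) score at Week 12".
- Section 4.2 places the "Patient Reported Index (ESSPRI) score at Week 4, 8, and 12" among the secondary endpoints.
- Section 9.1 justifies the sample size for the "primary efficacy endpoint (i.e. ESSDAI change from baseline at Week 12").
- Section 9.3.4.1, on the primary efficacy analysis, says "A MMRM (ESSDAI) will be used to compare treatment groups".

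The SAP, based on protocol version 7.0 (SAP Section 2.4), uses ESSDAI for the primary endpoint, the sample-size justification, the primary estimand and the primary efficacy parameter (Sections 2.2.1, 2.6, 3 and 6.2.2).

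On departures, protocol Section 9 states "Any deviations from the CSP are to be justified in the SAP". SAP Section 6.6 records two: the renaming of Ctrough to Ctau and a replacement prednisolone conversion table. SAP Section 1 adds that, because the study was stopped early, "only the primary endpoint and safety analyses will be performed".

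**The concern.** The estimand section exists to say exactly what is to be estimated, so a wrong variable there is not trivial on its face. ESSPRI is also a real Week 12 measurement in this trial. The sentence therefore reads as valid on its own, and the primary objective, worded in terms of signs and symptoms, does not expose it.

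If Section 5.6 were right, the primary question would concern a patient-reported score for which the protocol gives no SD and no target difference. After the early stop, that score would fall outside the analyses still to be done. If Section 5.6 is wrong, the SAP differs from the protocol on the primary estimand without saying so, despite the protocol's own rule on deviations. Either way, a reader comparing the abbreviated study report with Section 5.6 would find a mismatch that neither document explains.

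**Working it through.** The point is textual. The operating-characteristics table in protocol Section 9.1 is stated for ESSDAI and does not depend on Section 5.6, so there is no figure to recompute.

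**Step 1: where each score is the primary efficacy variable.**

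| Variable | Protocol | SAP | Total |
|---|---|---|---|
| ESSDAI | synopsis endpoint table, 4.1, 9.1, 9.3.4.1 | 2.2.1, 2.6, 3, 6.2.2 | 4 + 4 = 8 |
| ESSPRI | 5.6 | none | 1 + 0 = 1 |

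The synopsis paragraph on efficacy analysis also ties the MMRM to ESSDAI, but does not itself label ESSDAI as primary, so it is not counted.

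**Step 2: was it a deliberate change?** The change summaries for all six amendments list the sections affected. None lists Section 5.6, so no decision to move the estimand to ESSPRI is on record.

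**Step 3: do the design figures fit ESSPRI?** Section 9.1 uses reference differences of -5, -3 and -2 with SD 4.

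- ESSPRI is a mean of three 0–10 scales, with improvement defined as at least 1 point or 15% of baseline. A difference of 5 would be 5/10 = 50% of the scale and 5/1 = 5 times the one-point threshold.
- ESSDAI runs from 0 to 123, with a clinically meaningful reduction of at least 3 points. The reference values -5, -3 and -2 lie around that threshold.

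The numbers were chosen for ESSDAI, as Section 9.1 says.

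**Step 4: the two statements of the estimand side by side.**

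| Attribute | Protocol 5.6 | SAP 3 |
|---|---|---|
| Analysis set | FAS (randomized, at least one dose) | same |
| Variable | ESSPRI change, Week 12 | ESSDAI change, Week 12 |
| Early treatment discontinuation | hypothetical | same |
| Other intercurrent events | treatment policy | same |
| Summary | least-squares mean from MMRM | difference in least-squares means (MMRM, SAP 6.2.2.2) |

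Apart from the variable, the SAP only makes the summary explicit as a between-group difference. The acronyms ESSDAI and ESSPRI differ in two letters. Section 5.6 itself sends the reader to the SAP for details.

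**Step 5: what would change if the word were corrected?** The planned 20 + 10 = 30 subjects, SD 4, the MMRM, the two-sided 10% level and the visit schedule are already set out with ESSDAI as the primary endpoint. The correction changes none of them.

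**The case for a change.** The best case for acting is that the sponsor's rule covers any deviation, not only those that alter output, and that Section 6.6 already logs something as slight as a renamed trough concentration. On that standard, a different variable in the primary estimand deserves a line. The timing adds to this: the only SAP version is dated 17-Dec-2021, after the 26 November 2021 recommendation to terminate, so a written note would forestall any suggestion that the primary variable was switched late.

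Part of this stands. The difference between protocol Section 5.6 and SAP Section 3 is not recorded anywhere, and a note would fit the sponsor's own practice. The rest is weaker:

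- Section 6.6 is headed as a list of changes to planned analyses. The analysis planned in protocol Section 9.3.4.1 was an MMRM on ESSDAI, and the SAP keeps it. Where the protocol contradicts itself and the SAP follows its endpoint, sample-size and analysis sections, calling that a deviation is a matter of interpretation.
- A late switch is ruled out by the protocol, since version 7.0 of 12-May-2021 already named ESSDAI in Section 4.1.
- SAP Section 1 does give the reason why secondary endpoints such as ESSPRI will go unreported, namely the early termination.
- The lack of a sample-size basis arises only if Section 5.6 is read without Section 9.1.

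**Conclusion.** The inconsistency is certain, and it is a clerical slip: one place against eight, with no amendment behind it and design figures that suit only ESSDAI. The SAP, the later and more detailed document, states the estimand correctly, so the analysis is not ambiguous. The effect on sample size, data, model, output and interpretation is nil. Reopening a final SAP for a stopped study to log the slip would gain nothing in the results; authors of the abbreviated report can say in a sentence that Section 5.6 is read as ESSDAI. No change to the plan is needed.

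This conclusion assumes that the analysts work from SAP Sections 3 and 6.2.2. It does not rely on the grey shading that SAP Section 1 uses for provisions no longer applicable, because that shading is not visible in the text available here.
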